There are sufficient data showing OCT to be a useful tool to identify intravascular thrombi in patients with chronic thromboembolic pulmonary hypertension, together with an increase in vessel wall thickness in most patients with pulmonary hypertension^{12,13}.

Aim of the study

To evaluate by intravascular OCT study the presence of microvascular pulmonary thrombosis in patients with COVID-19, high D-dimer levels and contrast CT scan negative for pulmonary thrombosis. We'll also evaluate the extension of microvascular pulmonary thrombosis in patients with contrast CT scan positive for pulmonary embolism in areas where contrast CT scan was negative.

Inclusion Criteria (part A)

- Age ≥ 18
- Severe pulmonary coronarvirus disease 19 (COVID 19) with suspect for MicroCLOTS
 (microvascular COVID-19 lung vessels obstructive thromboinflammatory syndrome) AND
- Contrast CT scan negative for pulmonary thrombosis AND
- D-Dimer $> 10 \text{ mcg/mL } \mathbf{OR}$
- 5 < D-dimer < 10 mcg/mL and either C Reactive Protein (CRP) > 100 mg/dL or IL-6 > 6 pg/mL or ferritin > 900 ng/L

Inclusion Criteria (part B)

- Age ≥ 18
- Severe pulmonary coronarvirus disease 19 (COVID 19) with suspect for MicroCLOTS (microvascular COVID-19 lung vessels obstructive thromboinflammatory syndrome) **AND**
- Contrast CT scan positive for pulmonary thrombosis

Exclusion Criteria

- Age < 18
- Pregnancy or breastfeeding
- Known allergy to iodinated contrast dye
- Hemodynamic instability
- Glomerular Filtration rate < 30 ml/min
- Active bleeding or absolute contraindication to anticoagulant therapy

OCT procedure

- Femoral vein echo-guided puncture; 6 Fr 11 cm sheath insertion.

- Unfractionated heparin administration (70 100 U/kg) to achieve an activated clotting time (ACT) between 250 and 300 seconds.
- Pulmonary artery cannulation with 5 Fr Multipurpose (MP) catheter (Cordis, Dublin, Ohio) and Storq wire (Cordis).
- Pulmonary artery pressure measurement
- Selective pulmonary artery cannulation and angiography
 - The choice of the pulmonary arteries to be cannulated will be driven by "ground glass" area at CT scan
- 5Fr MP catheter will be changed for 6Fr MP guiding catheter over the Storq wire.
- Storq wire removal and 0.014" Balance wire distally advanced.
- OCT images acquisition

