 - In order to remove all the blood, as well as to obtain clear images, iodinated contrast is infused at a flow rate of 5 mL/s over 4 s, at 400 psi of pressure (Acist, Eden Prairie, Minnesota). Automatic pullback at 20 mm/s.
- If needed, blood samples can be taken through Recover catheter (Hexacath, Rueil-Malmaison, France)
- The same procedure will be performed:
 - o on "healthy" (without ground glass appearance at CT scan) area in the same lung
 - o on contralateral lung, both in "ground glass" and "healthy" areas according to CT scan.

PRIMARY ENDPOINT

- Overall safety of OCT procedure in COVID-19 pneumonia patients
- Presence of microvascular pulmonary thrombosis at OCT assessment in COVID-19 patients, both in "ground glass" and "healthy" ventilated areas.

SECONDARY ENDPOINT

- Pulmonary artery vessel anatomy characterization in COVID-19 patients
- Correlations with single trans-thoracic echocardiography (TTE) pulmonary hypertension (PH, estimated systolic pulmonary artery pressure > 35 mmHg) and right ventricular disfunction (RVD: tricuspid annular plane systolic excursion < 17 mm or Doppler tissue imaging S wave < 9.5 cm/sec).
- Dynamic correlations with standard inflammatory, coagulation and tissue damage

Study design, sample size, statistical analysis

The study is an open label, prospective, interventional clinical study of the safety, tolerability and potential diagnostic value of optical coherence tomography for microvascular lung vessels obstructive thromboinflammatory syndrome assessment in patients with COVID-19 pneumonia. This is a proof of concept exploratory study and will be conducted in 10 patients with mild-to-severe

The sample size calculation was designed for safety assessment based on a reference population of last 100 patients who underwent OCT at our Institution for coronary Artery Disease (CAD) in which a rate of SAEs lower than 1% have been recorded (personal communication)

Primary endpoint

ARDS.

As for safety analysis, the number of imaging related complications (expected/unexpected) and serious events (SAEs) (expected/unexpected and/or related/not related) and the percentage of subjects experiencing imaging related event (IRE) and SAEs in the study will be summarized by severity and within body system involved. Narratives will also be presented.

Secondary endpoints

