Continuous variables will be summarized with indices of location (i.e. mean or median) and dispersion (i.e. standard deviation or interquartile range), as appropriate. All relevant estimates will be reported with the corresponding 95% Confidence Intervals (CI).

Patients will be censored at study closure, withdrawn of consent or loss to follow-up.

Withdrawal and Premature Termination or Suspension of Study

Investigators may terminate a study subject's participation in the study if:

- Any clinical AE, or other medical condition or situation occurs such that continued participation in the study would not be in the best interest of the subject.
- The subject meets an exclusion criterion, either newly developed or not previously recognized (except those caused by ARDS and SARS-CoV-2 infection), that precludes further study participation.

This study may be suspended or prematurely terminated if there is sufficient reasonable cause. Written notification, documenting the reason for study suspension or termination, will be provided.

Circumstances that may warrant termination include, but are not limited to:

• Determination of unexpected, significant, or unacceptable risk to subjects;

Adverse events (AE)

AE is defined as any untoward medical occurrence in a patient or clinical investigation subject who underwent to a clinical procedure regardless of its causal relationship to the clinical procedure itself. An AE can therefore be any unfavorable and unintended sign (including an abnormal laboratory finding), symptom, or disease temporally associated with the performing of the clinical procedure. The occurrence of an AE may come to the attention of study personnel during the hospitalization period, or during follow up visits and interviews of a study subject presenting for medical care, or upon review by a study monitor.

Each AE will be recorded only once on the "Adverse Event" CRF page, with seriousness and maximum intensity that occurred over the duration of the event. Each event will also be evaluated with respect to causality and actions taken. All AEs will be monitored and recorded throughout the study. For all adverse events that require the subject to be discontinued from the study, the event(s) will be followed until final resolution or stabilization of the event(s).

The Investigator will classify and evaluate each AE as follows:

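### Does the sample size of 10, said to come from a safety calculation, need to be justified or changed because no target is stated?

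*Protocol*

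**What the plan says.** All of the sample size text is in the protocol section Study design, sample size, statistical analysis. It sets the size and the nature of the study together: "This is a proof of concept exploratory study and will be conducted in 10 patients with mild-to-severe" ARDS. The next sentence gives the rationale: "The sample size calculation was designed for safety assessment based on a reference population of last 100 patients who underwent OCT" for coronary artery disease at the same institution, "in which a rate of SAEs lower than 1% have been recorded", with a personal communication as the source. The protocol states no target rate, interval width, detection probability, significance level or power.

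Safety is the first-listed primary endpoint: "Overall safety of OCT procedure in COVID-19 pneumonia patients". Its analysis, under the Primary endpoint subheading of the same section, is descriptive. It covers the number of imaging complications and SAEs (expected or unexpected, related or not related) and "the percentage of subjects experiencing imaging related event (IRE) and SAEs in the study", summarised by severity and body system, with narratives. The following subsection, Secondary endpoints, says that relevant estimates will carry 95% confidence intervals.

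**The concern.** The protocol does more than choose a small number for practical reasons. It says that a calculation was made and that safety drove it. A reader who tries to retrace it finds one numerical input, a rate below 1%, and no target to go with it.

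The input also comes from another setting. The reference patients had coronary imaging. This study images pulmonary arteries in patients described under Inclusion Criteria (part A) as "Severe pulmonary coronarvirus disease 19 (COVID 19) with suspect for MicroCLOTS". Adverse events are counted "regardless of its causal relationship to the clinical procedure itself", so events due to the disease itself will enter the SAE count.

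What is at stake is how a clean result is read. If none of 10 patients has an event and the report sets this beside a reference rate below 1%, a reader might conclude that the procedure has been shown to be as safe as coronary OCT. Ten patients cannot show that.

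**Working it through.** **Inputs.** N = 10, one group, and a reference SAE rate below 1% in 100 patients, all from Study design, sample size, statistical analysis. I take p = 1% as the upper end of the stated range. If each patient counts once, below 1% means 0 of 100, whose own exact two-sided 95% upper limit is 1 − 0.025^(1/100) = 3.6%.

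**Step 1: can 10 be reproduced?** With no stated target there is no single formula to apply. Some usual goals at p = 1% give far more than 10:

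- At least one event with probability 80%, 90% or 95%: n ≥ ln(1 − q)/ln(0.99), giving 161, 230 or 299.
- An upper limit at or below 1% after 0 of n: ln(0.05)/ln(0.99) gives 299 (one-sided 95%); ln(0.025)/ln(0.99) gives 368 (two-sided 95%).

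Other goals that use the 1% rate do give 10:

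- At least a 90% chance of no event: 0.99^10 = 0.904 and 0.99^11 = 0.895, so 10 is the largest such n.
- A normal-approximation 95% half-width of about 6.2 points: 1.96 × √(0.01 × 0.99/10) = 0.0617. The approximation is poor at this rate, but it is often used.
- A single-arm exact test of 1% against 15%, rejecting on one or more events: type I error 1 − 0.99^10 = 9.6%, within a one-sided 10%; power 1 − 0.85^10 = 80.3%.

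The protocol states none of these goals. The result is therefore undetermined: 10 cannot be verified, and it cannot be called wrong. Nor can one say that 10 arises only from event rates far above 1%.

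**Step 2: what do 10 patients show?**

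| True event rate | P(no event in 10) = (1 − p)^10 | P(at least one) |
|---|---|---|
| 1% | 90.4% | 9.6% |
| 5% | 59.9% | 40.1% |
| 10% | 34.9% | 65.1% |
| 20% | 10.7% | 89.3% |

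Exact (Clopper-Pearson) two-sided 95% intervals are 0 to 30.8% for 0 of 10, where the upper limit is 1 − 0.025^(1/10), and 0.3% to 44.5% for 1 of 10. The one-sided 95% upper limit for 0 of 10 is 1 − 0.05^(1/10) = 25.9%. A clean result therefore does not exclude a 20% event rate under either convention.

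**Step 3: does any result or decision depend on the missing target?** The primary safety analysis produces counts, percentages and narratives. There is no hypothesis test, no comparison with the coronary series, no margin and no numerical stopping rule. The grounds for terminating the study are qualitative and refer to unexpected, significant or unacceptable risk. Whatever target the sponsor had in mind, the same 10 patients would be studied and the same percentages reported.

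**The case for a change.** The strongest case for a change is that a pragmatic sample size needs no calculation, but a claimed calculation should be traceable. A statistical analysis plan could not fully cure this, because the protocol itself gives the basis, and that basis alone does not lead to 10. Safety heads the list of primary endpoints. The 95% interval sentence sits under Secondary endpoints, so it is arguable whether it covers the safety percentages. A rewording would cost nothing.

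Part of this stands. The sentence cannot be retraced, the coronary rate is a weak guide to this population, and 0 of 10 is weak evidence of safety.

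The rest carries less weight:

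- The protocol openly names the coronary setting, so no reader is misled about where the rate comes from.
- All-cause counting does not hide procedural harm. SAEs are split into related and not related, each adverse event is given a relationship to the intervention, and imaging-related events have their own definition. How SAEs were counted in the coronary series is not documented, so a mismatch in counting is possible but not shown.
- The interval sentence speaks of all relevant estimates. An analyst reporting a primary safety percentage from 10 patients would sensibly attach an interval, and the choice of an exact method is a detail that a statistical analysis plan commonly holds.

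**Conclusion.** No change to the plan follows. The observation is accurate as far as it goes: a safety-based calculation is claimed, its target is not stated, and 10 can be neither confirmed nor refuted. It is a gap in the rationale of a small exploratory study. It is not a fault in the design, and filling it would change no result.

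The practical size of the issue is the precision of 10 patients: a two-sided 95% upper limit of 30.8% after 0 events, and an interval of 0.3% to 44.5% after 1. This follows from N = 10 whatever reason is given for it, and it is a fair trade-off for a first look at an invasive imaging procedure in this population.

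The conclusion rests on three conditions: the safety analysis stays descriptive, as the protocol has it; the 1% figure is not used as a comparator when results are reported; and the safety percentages are given with confidence intervals, as the Secondary endpoints text can reasonably be read to require. If a formal comparison with the coronary rate were planned, the missing target would matter.

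### Do the withdrawal rules let later SAEs or deaths go unrecorded once an investigator ends a patient's participation?

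*Protocol*

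**What the plan says.** Under Withdrawal and Premature Termination or Suspension of Study, the protocol gives two permissive grounds on which an investigator may end a subject's participation. The first is broad and covers any cause: "Any clinical AE, or other medical condition or situation occurs such that continued participation in the study would not be in the best interest". The second concerns an exclusion criterion that turns out to apply: "either newly developed or not previously recognized (except those caused by ARDS and SARS-CoV-2 infection), that precludes further study participation". The Exclusion Criteria include "Glomerular Filtration rate < 30 ml/min", "Active bleeding or absolute contraindication to anticoagulant therapy" and haemodynamic instability.

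Three other places bear on what happens to the data.

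- Adverse events (AE): "All AEs will be monitored and recorded throughout the study". The same section adds: "For all adverse events that require the subject to be discontinued from the study, the event(s) will be followed until final resolution or stabilization". It defines an adverse event by reference to a person who had the procedure, and names the hospital stay, follow-up visits, interviews and monitor review as ways in which events come to light.
- Study design, sample size, statistical analysis, under Secondary endpoints: "Patients will be censored at study closure, withdrawn of consent or loss to follow-up".
- Imaging-related events: the operator registers events during imaging, and major peri-procedural events (death, acute kidney injury, major bleeding, contrast reaction, access-site complications) are recorded as well.

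The planned safety summary gives event counts, narratives and "the percentage of subjects experiencing imaging related event (IRE) and SAEs in the study will be summarized by severity and within body system involved".

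**The concern.** Good practice separates stopping an intervention from stopping observation, and the withdrawal section does not do so. The intervention here is one catheterisation session, so for a patient already imaged there is little left of participation except follow-up. Ending participation could then be read as ending safety collection.

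The grounds for termination also overlap with the outcomes. Low filtration rate and active bleeding are exclusion criteria, while acute kidney injury and major bleeding are events to be recorded. The procedure uses heparin and iodinated contrast and could plausibly contribute to either. Under the second ground, a criterion caused by the procedure can lead to termination, while the same condition caused by COVID-19 is exempt. If termination did stop data collection, the loss would be related to safety.

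The only sentence that expressly reaches past discontinuation covers the triggering event alone. A later, separate SAE or death is not named. Nor is the patient who is terminated with no triggering adverse event, for example because a criterion had been overlooked at entry. With 10 patients, one missed event moves a percentage by 1/10, or 10 points.

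**Working it through.** The protocol has no figure of its own on this point to reproduce. The check is a reading of the text by time of termination, followed by the arithmetic of the worst case.

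**Step 1: where could an event be lost?**

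1. *Termination before the procedure.* There is no exposure to OCT, so no procedural safety event can be lost.
2. *Termination during the procedure.* Imaging-related events are intra-procedural and logged by the operator. Later withdrawal cannot remove them.
3. *Termination afterwards because of an adverse event.* That event is recorded and followed to resolution or stabilisation, and death is one of the outcome categories. Only a later, separate event depends on other text.
4. *Termination afterwards with no triggering adverse event.* The follow-up sentence does not apply. Any later event depends on other text.

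Only later separate events in cases 3 and 4 are in question.

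**Step 2: what does the other text say about them?**

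- The censoring sentence names study closure, withdrawn consent and loss to follow-up. Investigator termination is absent, so on its natural reading a terminated patient who has not withdrawn consent is not censored. The sentence stands under the secondary endpoints but is worded for patients in general.
- The instruction to record all adverse events throughout the study, the definition of an adverse event and the routes by which events come to light are not tied to participation status.
- The list of major peri-procedural events has no exception for terminated patients.
- The ARDS/SARS-CoV-2 exception narrows one permissive ground. The other ground has no such limit, so the exception does not decide whose data are kept.

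**Step 3: size of the worst case.**

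Inputs: n = 10 (Study design, sample size, statistical analysis). The protocol states no withdrawal rate. Assumed for illustration: one patient terminated after the procedure, one later separate death in that patient, that death not recorded, and no SAE in the other nine.

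Exact (Clopper-Pearson) 95% limits:

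- For 0/n the upper limit is 1 − 0.025^(1/n). With n = 10 this is 0.3085, and with n = 9 it is 0.3363.
- For 1/10 the lower limit is 1 − 0.975^(1/10) = 0.0025. The upper limit p solves (1 − p)^10 + 10p(1 − p)^9 = 0.025, which gives p = 0.4450.

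| Case | Quantity | Reported | True |
|---|---|---|---|
| (a) reason for termination was an SAE | patients with any SAE | 1/10 (0.3 to 44.5%) | 1/10 (0.3 to 44.5%) |
| (a) | SAE count | 1 | 2 |
| (a) | deaths | 0/10 (0 to 30.8%) | 1/10 (0.3 to 44.5%) |
| (b) reason was not an SAE, or no adverse event | patients with any SAE | 0/10 (0 to 30.8%) | 1/10 (0.3 to 44.5%) |
| (b) | deaths | 0/10 (0 to 30.8%) | 1/10 (0.3 to 44.5%) |
| (a) and (b) | imaging-related events | unchanged | unchanged |

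Dropping the patient from the denominator as well would give 0/9 (0 to 33.6%), but nothing in the protocol suggests that exclusion.

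The chance of the loss is P(termination after the procedure) × P(later separate event, given termination) × P(not recorded, given both). The protocol supplies none of the three. If the censoring sentence is followed, termination itself gives no reason for the last to be above zero.

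**The case for a change.** The best case for a change is that an analysis plan cannot recover data that were never collected, so the duration of safety collection is a protocol matter. The recording instruction has no end date per patient. If it already reached past termination, the separate sentence on events leading to discontinuation might seem to add little. The withdrawal section ends participation without referring to the censoring sentence, so staff could act either way, and one or two sentences would settle it.

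Part of this stands. The silence is real, and post-termination collection does belong in a protocol. The inference from the follow-up sentence is weak, however. That sentence follows an event to its own end, with no limit at study closure, so it has a purpose even if general recording continues after termination. The two possible readings are also not equally supported: the proposed wording would only restate what the censoring sentence already implies.

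The protocol also gives no length for adverse event follow-up. That applies to all 10 patients alike and does not arise from the withdrawal rules.

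**Conclusion.** No change is needed. No stated rule is shown to give a wrong result, and no two passages contradict each other. One matter is left implicit, and the surrounding text points to the sensible answer: keep recording SAEs and deaths in every patient who had the procedure, unless consent is withdrawn or the patient is lost.

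On that reading the effect on the safety results is nil. On the unfavourable reading it is at most one death and one SAE per terminated patient. In the illustration, the any-SAE result reads 0/10 rather than 1/10, and only if the reason for termination was not itself an SAE. Imaging-related events are untouched.

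The conclusion rests on two assumptions: that the censoring sentence applies to safety data as well as to the secondary endpoints, and that a team following 10 patients with severe disease, at least while in hospital, would record a death or SAE that came to its notice.

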- Description of event (if the event consists of a cluster of signs and/or symptoms, record a diagnosis [e.g.: "flu"] rather than each sign and symptom)
- Onset date
- Stop date (if resolved)
- Seriousness (see definition of serious adverse events below)
- Intensity ("Mild" [does not interfere with daily activities]; "Moderate" [interferes with daily activities]; "Severe" [prevents daily activities])
- Relationship to study intervention (Not Related, Possibly Related, Probably Related)
- Action taken (None, Required concomitant treatment, Permanent discontinuation of study intervention, Other [explain])
- Outcome (recovered without sequelae, Resolved with sequelae, Ongoing, Unknown, Death)

Serious Adverse Events (SAE)

An SAE is an AE that meets 1 or more of the following criteria:

- Results in death
- Is immediately life-threatening (places the subject at immediate risk of death from the event as it occurred)
- Requires or prolongs in-patient hospitalization
- Results in a persistent or significant disability or incapacity
- Results in a congenital anomaly or birth defect or malignancy
- Is medically important
- Requires medical intervention to prevent permanent impairment or damage

Imaging-related events

Intra-procedural adverse events will be recorded and considered as potential imaging-related events (IRE). IRE will be defined as the occurrence of clinical symptoms (worsening of respiratory failure, requiring invasive mechanical ventilation, hemoptysis), adverse angiographic outcomes (dissection, perforation, vasospasm, thrombus formation, abrupt closure), requiring interruption of the imaging procedure during intra-polmonary imaging and will be routinely registered by the operator. Major peri-procedural adverse events will be also be recorded: death, acute kidney injury, major bleedings, contrast media reaction, access-site related complications.

Fundings: The procedure will be covered by SSN. The other costs (see attached table of costs) will be covered by COVID BIOB funds.

REFERENCES

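### The protocol's only adverse event intensity scale rests on daily activities, which suits neither inpatients with severe COVID-19 nor intra-procedural findings, so the severity breakdown of the primary safety results will be subjective

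*Protocol*

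**What the plan says.** The Protocol section on adverse events has the investigator classify every event on several items. One is intensity, in three grades: an event is mild if it "does not interfere with daily activities", moderate if it does interfere, and severe if it makes those activities impossible. The maximum intensity over the event goes on the case report form, with seriousness as a separate item. No other scale of degree appears in the protocol.

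The first primary endpoint is "Overall safety of OCT procedure in COVID-19 pneumonia patients". In the statistical analysis section, under the primary endpoint, "the percentage of subjects experiencing imaging related event (IRE) and SAEs in the study will be summarized by severity", and also by body system. The same paragraph adds: "Narratives will also be presented".

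Both parts of the study enrol patients with "Severe pulmonary coronarvirus disease 19 (COVID 19) with suspect for MicroCLOTS". The study design section describes 10 patients with ARDS of mild to severe degree. Adverse events may come to light during the hospital stay and also at follow-up visits and interviews.

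**The concern.** A grade based on daily activities works when the patient has a usual routine that an event can disturb. Many patients here will be in hospital with severe lung disease, and the scale names no reference level of activity for them. The events of most interest for the safety of optical coherence tomography arise during the procedure itself, where no daily activity is under way.

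At stake is one prespecified part of the primary safety report. If two investigators can follow the text and give the same event different grades, the breakdown by severity says as much about the grader as about the procedure. The study is open label, so a subjective grade is also more exposed to expectation.

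**Working it through.** No planned figure is in dispute, so the check sets the sections side by side.

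**1. Does the severity summary use this scale?** The analysis section says severity and the adverse event section says intensity. The protocol does not state that they are the same, but it offers no other graded measure. The natural reading is that "will be summarized by severity and within body system involved" refers to the intensity item.

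**2. Can the scale be applied consistently to a patient who is already limited?** Two readings fit the text:
- *Actual change:* how far did the event reduce what this patient was doing just before it? For a patient confined to bed, even a substantial event may change nothing, which gives mild.
- *Hypothetical effect:* how far would the event disturb a person with ordinary activities? The same event could then be moderate or severe.

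The protocol does not choose between them, so the grade depends on the investigator.

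**3. Can the scale be applied to the events being counted?** This step needs no assumption about baseline function.

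| Event type | Where the protocol names it | Link to daily activities |
|---|---|---|
| Vasospasm, perforation, dissection, thrombus, vessel closure | Imaging-related events | None direct; found during imaging |
| Abnormal laboratory result | Adverse events (definition) | None direct |
| Acute kidney injury | Imaging-related events (major peri-procedural events) | Often indirect |
| Haemoptysis, worsening respiratory failure | Imaging-related events | Possible, but the reference level is undefined (step 2) |

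**4. Do other recorded items supply the missing degree?**
- *Seriousness* is yes or no. Every SAE is serious by definition, so seriousness cannot split SAEs by severity.
- *IRE status* is also yes or no: a listed event that required imaging to be interrupted.
- *Named categories* give the type of event. A dissection may be limited or extensive.
- *Action taken and outcome* are informative, but the plan does not tabulate by them.
- *Narratives* describe individual events but do not repair the table.

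**5. How many events might the table hold?** This is context only. The protocol cites an SAE rate below 1% in 100 coronary patients. If 1% applied here, the chance of at least one SAE in 10 patients would be 1 − 0.99^10 = 1 − 0.904 = 0.096, or 9.6%. The rate in this population is unknown, and SAEs unrelated to imaging also count, so the true chance may be well above this. If procedure-related events are few, each grade carries weight and the narratives will carry much of the detail.

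**The case against.** The strongest defence is that the protocol records enough besides intensity to tell a trivial event from a grave one. Much of it stands.

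- *The primary counts do not use the grade.* Numbers of imaging complications and SAEs, and percentages of patients affected, are the same whatever the intensity item says. A reader might infer that the whole safety endpoint is compromised; the text does not support that.
- *Seriousness is judged on the event, not the patient.* A reader might infer that these patients already meet the SAE criteria by being in hospital and critically ill. The criteria ask whether the event itself put life at immediate risk, or led to or lengthened the hospital stay. Illness before the procedure satisfies neither, so seriousness keeps its meaning. It remains binary.
- *Major bleeding and access-site problems are recorded by name.* A small haematoma and a large bleed would be distinguishable in the record even with the same intensity grade.
- *The scale is not at its ceiling before the procedure.* It grades what the event does. Calling a minor event severe because COVID-19 already prevents activity would attribute the disease's effect to the event. What remains is an undefined reference level.
- *The protocol does not say that patients perform no daily activities.* The ARDS range includes mild disease, haemodynamic instability is an exclusion, and a need for invasive ventilation is listed as a possible event, which implies that some patients enter without it. Events found at follow-up may be graded as intended.

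It can also be said that the SAP, which is not shown, could specify the tabulation. It could, but the protocol already fixes the definition the investigator applies at the bedside, and an analysis plan cannot readily recover a degree that was not recorded consistently.

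**Conclusion.** The point holds in limited form. The only intensity scale in the protocol fits these patients and the intra-procedural events poorly, so the breakdown of IREs and SAEs by severity will be subjective and will discriminate poorly. The documents do not support saying that mild and severe events cannot be told apart at all.

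The defect affects one breakdown within a primary endpoint and changes no planned figure. The protocol gives no proportion of patients unable to carry out daily activities, so none is estimated here. The conclusion rests on two assumptions: that severity in the analysis section means the intensity item, and that many patients are limited in activity at entry. The argument from intra-procedural and laboratory findings does not need the second. A change is worth making because it is cheap and because grades assigned under the present wording may be hard to reconstruct later.

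**What to change.** Before enrolment, replace the daily-activities wording in the adverse event section with grades defined by clinical findings and by the level of intervention the event required; a CTCAE-type scale is one example. State that the grade is judged as change from the patient's state just before the procedure. Include explicit entries for intra-procedural angiographic findings and for laboratory abnormalities. In the statistical analysis section, say that the summary by severity uses this grade, so that the two terms are tied together. Leave the seriousness criteria, the named events and the narratives as they are.

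The cost is wording in the protocol and the case report form, with no extra patients, procedures or measurements. The one downside is a longer grading table for investigators.
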